**Appendix 10: Management Guidelines for Cytokine Release Syndrome**

**Table 1 Management Guidelines for Cytokine-Release Syndrome (cont.)**

Event a	Action to Be Taken
Grade 2 (cont.)	
Restarting infusion:
 
 
• Wait until 30 minutes after the event has resolved before restarting the infusion at up to 25% of the original infusion rate.
 
• If hypotension or hypoxia recurs, stop infusion immediately. Study medication should not be re-administered (re-started) again during this cycle.               
 
– If hypotension or hypoxia recurs, manage as a Grade 3 event.
 
 
 
 
Next cycles:
 
 
• May receive the next dose of study medication if symptoms resolve to Grade <math>\leq</math> 1 for 3 consecutive days with approval of Medical Monitor, as follows:               
 
– Pretreat with antihistamines, antipyretics and/or analgesics as clinically indicated.
 
– Pretreat with IV corticosteroids (methylprednisolone 80 mg or dexamethasone 16 mg) at least 60 minutes prior to the administration of study medication
 
– Administer study medication at 50% of the initial infusion rate of the previous cycle.
 
 
 
 
Subsequent cycles:
 
 
• If there is an occurrence of IRR or CRS Grade <math>\geq</math> 3 in any of the subsequent cycles, permanently discontinue study medication regardless of recovery (see Grade 3 management guidelines).
 
• If there is an occurrence of a Grade <math>\leq</math> 2 CRS in subsequent cycles, manage as indicated by severity (see Grade 1 or Grade 2 management guidelines).
 

**Appendix 10: Management Guidelines for Cytokine Release Syndrome**

**Table 1 Management Guidelines for Cytokine-Release Syndrome (cont.)**

Grade a	Action to Be Taken

Grade 3
 
Fever b ≥ 38°C with either:  Hypotension – requiring a single vasopressor (with or without vasopressin) and/or  Hypoxia – requiring > 6 L/min oxygen by nasal cannula, facemask, non-rebreather mask, or Venturi mask to maintain oxygen saturation
 
Organ toxicity: Grade 3 organ toxicity or Grade 4 transaminitis
	
Immediate actions:
 
 
• Stop further infusion of study medication
 
• Admission to ICU is recommended
 
• Treat symptomatically as indicated, including antihistamines, antipyretics, and/or analgesics as needed.
 
• Provide other supportive care as clinically indicated (e.g., fever and neutropenia, infection).
 
• Monitor fluid balance; administer IV fluids as clinically indicated.
 
• Treat with IV corticosteroids (methylprednisolone 2 mg/kg/day or, if neurologic symptoms are present, dexamethasone 10 mg).
 
• Consider anti-cytokine therapy.
 
• Monitor cardiac and other organ function closely.
 
• Provide oxygen for hypoxia.
 
• Notify Medial Monitor.
 
• Initiate work-up and assess for signs and symptoms of MAS/HLH. c
 
 
Restarting infusion:
 
 
• Study medication should not be administered again during this cycle.
 

**Appendix 10: Management Guidelines for Cytokine Release Syndrome**

**Table 1 Management Guidelines for Cytokine-Release Syndrome (cont.)**

Grade a	Action to Be Taken
Grade 3 (cont.)	
Next cycle:
 
 
• If the patient had a Grade <math>\geq</math> 2 IRR or CRS in any previous cycle, permanently discontinue study medication.
 
• If patient does not recover (is febrile or still on vasopressors) within 8 hours after corticosteroid and anti-cytokine treatment, permanently discontinue study medication.
 
• If patient recovers (is afebrile and off vasopressors) within 8 hours following corticosteroid and anti-cytokine treatment, study medication can be administered in next cycle, as follows:               
 
– Pretreat with antihistamines, antipyretics and/or analgesics as clinically indicated.
 
– Pretreat with IV corticosteroids (methylprednisolone 80 mg or dexamethasone 16 mg) at least 60 minutes prior to the administration of study medication.
 
– Hospitalize patient for 24 hours.
 
– Administer study medication at 50% of the initial infusion rate of the previous cycle. d
 
 
 
 
Subsequent cycles:
 
 
• If a Grade <math>\geq</math>3 CRS recurs, permanently discontinue study medication.
 
• If there is an occurrence of a Grade <math>\leq</math> 2 CRS in subsequent cycles, manage as indicated by severity (i.e., Grade 1 or Grade 2 management guidelines).
 

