**Table 3 Management Guidelines for Infusion-Related Reactions**

Event a	Management
IRR, Grade 1	
 
• Reduce infusion rate to half the rate being given at the time of event onset.
 
• After the event has resolved, the investigator should wait for 30 minutes while delivering the infusion at the reduced rate.
 
• If the infusion is tolerated at the reduced rate for 30 minutes after symptoms have resolved, the infusion rate may be increased to the original rate.
 

IRR, Grade 2	
 
• Interrupt study treatment infusion.
 
• Administer aggressive symptomatic treatment (e.g., oral or IV antihistamine, anti-pyretic medication, glucocorticoids, epinephrine, bronchodilators, oxygen, IV fluids).
 
• After symptoms have resolved to baseline, resume infusion at half the rate being given at the time of event onset.
 
• For subsequent infusions, consider administration of oral premedication with antihistamines, anti-pyretics, and/or analgesics and monitor closely for IRRs.
 

IRR, Grade 3	
 
• Stop infusion.
 
• Administer aggressive symptomatic treatment (e.g., oral or IV antihistamine, anti-pyretic medication, glucocorticoids, epinephrine, bronchodilators, oxygen, IV fluids).
 
• Subsequent infusions may be administered with premedication in consultation with and with approval of the Medical Monitor. b
 
• Patients who experience Grade 3 wheezing, bronchospasm, or generalized urticaria at first occurrence must be discontinued from study treatment.
 
 
Notes:
 
 
• If symptoms recur despite premedications with the same or greater severity at subsequent cycles, the infusion must be stopped immediately and patient permanently discontinued from study treatment.
 

IRR, Grade 4	
 
• Stop infusion.
 
• Administer aggressive symptomatic treatment (e.g., oral or IV antihistamine, anti-pyretic medication, glucocorticoids, epinephrine, bronchodilators, oxygen, IV fluids).
 
• Permanently discontinue study treatment and contact Medical Monitor.
 

IRR = infusion-related reaction.

a Refer to NCI CTCAE v5.0 for the grading of symptoms

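### Three mandatory stops for repeated infusion or cytokine reactions are written by cycle, so a Day 1 then Day 8 sequence within one cycle does not trigger them

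*Combined protocol and SAP*

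**What the plan says.** Infusions are given on Days 1 and 8 of each 14-day cycle, with a third in Cycle 1 of Arm B (Section 3.1.1; Appendix 1, footnote r). Three rules require permanent discontinuation:

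- **Recurrent Grade 3 IRR** (Section 5.1.2.2, Table 3): "If symptoms recur despite premedications with the same or greater severity at subsequent cycles".
- **Grade 3 or higher IRR or CRS after Grade 2 CRS** (Appendix 10, Table 1, Grade 2 row): an occurrence "in any of the subsequent cycles, permanently discontinue study medication regardless of recovery".
- **Grade 3 CRS with an earlier reaction** (Appendix 10, Table 1, Grade 3 row): a Grade 2 or higher "IRR or CRS in any previous cycle, permanently discontinue study medication".

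Permission to re-dose is mostly written by infusion or dose. After a Grade 3 IRR, further infusions "may be administered with premedication in consultation with and with approval of the Medical Monitor". After Grade 2 CRS the table says "May receive the next dose of study medication if symptoms resolve to Grade" 1 or lower for 3 consecutive days, with Medical Monitor approval. After Grade 3 CRS there is a ban, "Study medication should not be administered again during this cycle", but for a patient who recovers within 8 hours of corticosteroid and anti-cytokine treatment, "study medication can be administered in next cycle, as follows".

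**The concern.** The rules count in one unit and the drug is given in another. A second serious reaction at the very next infusion is the pattern these stops are meant to catch, yet whether they apply depends on which side of a cycle boundary that infusion falls. In a first-in-human trial that has already issued an Urgent Safety Measure for IRRs (Section 5.1.1.1), a rule meant to be mandatory becomes discretionary for some patients, and the protocol gives no safety reason for the difference.

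**Working it through.** No design figure is involved. The check applies each rule, as worded, to the dosing calendar.

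**Interval.** Day 1 to Day 8 is 8 − 1 = 7 days. Day 8 to the next Day 1 (day 15 of the count) is 15 − 8 = 7 days. The nominal gap is the same.

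**Sequences**, using cycles beyond any DLT window:

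| Two consecutive infusions | Cycle 3 Day 8, then Cycle 4 Day 1 | Cycle 3 Day 1, then Day 8 |
|---|---|---|
| Grade 3 IRR, then Grade 3 IRR despite premedication | Mandatory stop (Table 3) | No mandatory stop; further infusions need Medical Monitor approval |
| Grade 2 CRS, then Grade 3 CRS | Mandatory stop (Grade 2 and Grade 3 rows) | Neither row applies; next cycle open on 8-hour recovery |
| Grade 2 IRR, then Grade 3 CRS | Mandatory stop (Grade 3 row) | No event in a previous cycle; next cycle open on 8-hour recovery |
| Grade 2 CRS, then Grade 3 IRR | Mandatory stop (Grade 2 row) | No mandatory stop; Table 3 approval route |

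**Is the Day 8 dose allowed after the Day 1 event?** Yes, with conditions. After a Grade 2 IRR, Table 3 lets even the same infusion resume. After a Grade 3 IRR, it speaks of subsequent infusions. After Grade 2 CRS, the permission is for the next dose, and three consecutive days at Grade 1 or lower can fit within 7 days.

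**Could the current cycle count as a previous one in the Grade 3 CRS row?** That row's rule sits under a next-cycle heading, so one could try this. But then the Grade 3 CRS would itself be a Grade 2 or higher event in a previous cycle. Every such patient would have to stop, and the 8-hour recovery path would be empty. The only coherent reading excludes the current cycle.

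**Does the same-cycle ban close the gap?** After Grade 3 CRS on Day 1 (Cycle 2 onward, or Arms A and C in Cycle 1) it withholds 1 infusion (Day 8). After Grade 3 CRS on Day 8 it withholds 0, because Day 8 is the last infusion of the cycle.

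**Do the DLT rules close it?** The window is Cycle 1 Days 1–14 in Arms A and B, and Cycle 1 Day 8 to Cycle 2 Day 7 in Arm C (Section 3.1.1.1). In Cycle 1, a recurrent IRR that precluded full dosing is a DLT, and Grade 3 CRS on Day 8 would on its face be one, as a Grade 3 non-hematologic major organ event outside the listed exceptions. Dosing is then interrupted, but Section 3.1.2 allows restart at the prior cohort's dose. From Cycle 2 on, a second event on Day 8 is outside the window in every arm, unless the window was extended for a dose delay.

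**Size.** Section 5.1.1.1 reports Grade 2 IRRs in 1 of 3 and 2 of 2 patients, so (1 + 2)/(3 + 2) = 3/5 = 60% (exact 95% CI 15% to 95%), before corticosteroid premedication was mandated. This describes only a possible first event for the Grade 3 CRS rule. It is not the frequency of any full sequence, which the documents do not allow one to compute.

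**The case against.** The best opposing case is that re-dosing is well guarded. Continued treatment after a DLT or other treatment-related Grade 3 toxicity needs Medical Monitor approval, and the toxicity must resolve to Grade 1 or lower (Section 5.1.2.1). After a Grade 3 IRR, resumption may be considered only for patients deriving benefit and fully recovered, with documented approval (Table 3, footnote b). On-treatment response laboratory tests are first scheduled at Cycle 3 Day 1, so an earlier re-challenge would precede scheduled evidence of benefit. Management of Grade 3 or higher IRR or CRS is to be discussed at once with the Medical Monitor (Appendix 10), and the investigator or Sponsor must stop treatment judged to jeopardize safety (Section 4.6.1). Re-dosing after Grade 3 CRS also carries steroid pretreatment, 24-hour hospitalization and a halved rate. Grade 4 events, and Grade 3 wheezing, bronchospasm or generalized urticaria, already end treatment at first occurrence.

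All of this stands, and it narrows the exposure. A reader might infer that the wording lets patients be re-dosed automatically after a same-cycle recurrence; the documents do not support that. But for the sequences in the table these safeguards are judgements or pauses. They do not restore the mandatory stop. Dose reduction is only to be considered, and the recurrence stop in Section 5.1.2.1 applies only at a reduced dose.

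Two further extensions are tempting and should not be made.

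- **Arm B, Day 1 then Day 2.** A Grade 3 IRR stops the infusion. The express permission to go on to Day 2 after an incomplete Day 1 dose covers scheduling reasons with at least 75% given. Full recovery and benefit would also be needed within about a day.
- **The half rate.** "Administer study medication at 50% of the initial infusion rate of the previous cycle" names no single infusion. At Table 1 minimum times, constant rate, a 50/50 split in Arm B and the 14 mg/kg/hr limit not binding, a Cycle 2 Day 1 target dose T would run for 4 or 2 hours in Arm A (half of T/2 or of T per hour). In Arm B it would run for 8 or 4 hours (half of T/4 or of T/2 per hour). Both readings are slower than the 30-minute minimum, and no harm follows. Tying the rate to the infusion that caused the reaction would fail in Arm C: 60 mg over 2 hours is 30 mg/hr, half is 15 mg/hr, and illustrative Day 8 targets of 180 and 1180 mg would take 180/15 = 12 and 1180/15 = 78.7 hours.

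**Conclusion.** The concern holds for three rules: recurrent Grade 3 IRR, a Grade 3 or higher IRR or CRS after Grade 2 CRS, and Grade 3 CRS after an earlier Grade 2 or higher reaction. As worded, each misses a Day 1 then Day 8 sequence in one cycle and catches the same events 7 days apart across a boundary. This rests on a literal reading, with the current cycle excluded from previous cycles, and on nominal dosing days. In practice the exposure is Grade 3 second events, since Grade 4 already ends treatment. Section 5.1.1.1 calls the likelihood of CRS very low and reports no Grade 3 IRR in the five patients described, so few patients would be affected. It should be fixed, at low to moderate priority.

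**What to change.** - Table 3, Grade 3 IRR note: replace the reference to subsequent cycles with *at any subsequent infusion*.
- Appendix 10, Table 1, Grade 2 row: make the same replacement.
- Appendix 10, Table 1, Grade 3 row: replace the reference to a previous cycle with *at any infusion before the one that caused the Grade 3 event*.
- Keep the ban on further dosing in the same cycle after Grade 3 CRS, and leave the half-rate instruction out of this change.

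The cost is three edits in two tables, with no extra patients or data. The downside is that a few patients with a same-cycle recurrence would be discontinued earlier, as those whose recurrence crosses a cycle boundary already must be.

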**Appendix 10: Management Guidelines for Cytokine Release Syndrome**

**Table 1 Management Guidelines for Cytokine-Release Syndrome (cont.)**

Grade a	Action to Be Taken

Grade 4
 
Fever b ≥ 38°C with either: Hypotension – requiring multiple vasopressors (excluding vasopressin) and/or Hypoxia – requiring positive pressure (e.g., CPAP, BiPAP, intubation and mechanical ventilation) Organ toxicity: Grade 4 (excluding transaminitis)
	
Immediate actions:
 
 
• Follow all Grade 3 management guidelines.
 
• Permanently discontinue study treatment.
 

CRS = cytokine-release syndrome; HLH = hemophagocytic lymphohistiocytosis; ICU = intensive care unit; MAS = macrophage activation syndrome.

- a Modified CRS grading per ASTCT (Lee et al. 2019). Refer to [Appendix 9](#) for the complete description of grading of symptoms.
- b Fever is defined as temperature ≥ 38°C not attributable to any other cause. In patients who have CRS and then receive antipyretic or anti-cytokine therapy such as tocilizumab or steroids, fever is no longer required to grade subsequent CRS severity. CRS grade is determined by the more severe event: hypotension or hypoxia not attributable to any other cause.
- c Refer to [Appendix 12](#) for HLH/MAS diagnostic criteria.
- d If the patient does not experience CRS during the next infusion at the 50% reduced rate, the infusion rate can be increased to the initial rate in subsequent cycles upon discussion with Medical Monitor. However, if this patient experiences another CRS event, the infusion rate should be reduced by 25%–50% depending on the severity of the event.

## Appendix 11

### Modified Continuous Reassessment Method with Escalation with Overdose Control Design

Details of the mCRM-EWOC design used in the study are described in this appendix. In addition, the design operating characteristics are evaluated through comprehensive simulations in this section. In this study, the MTD is defined as the dose maximizing the posterior probability that the DLT rate belongs to [0.20,0.35], while keeping the probability of overdose below 0.25. The details of the mCRM-EWOC design will be described below. Calculations are done using R package crmPack 0.1.9 (<https://cran.rproject.org/web/packages/crmPack/index.html>).

#### **Dose-Response Model**

The probability of DLTs over doses (dose-DLT response curve) will be described by a two-parameter logistic regression model:

$$\text{logit}(p(d)) = \alpha + \beta \left( \frac{d}{d^*} \right)$$

where  $p(d)$  stands for the DLT rates under a dose level  $d$ , and  $d^*$  is set to 1200 mg in the study as the reference dose. Thus, the dose-DLT response curve follows a sigmoidal shape and can be flexibly adjusted by a parameter

$$\theta = \begin{pmatrix} \alpha \\ \log \beta \end{pmatrix} \sim N(\mu, \Sigma)$$

It is common to assume such a sigmoidal curve since usually the DLT rate increases monotonically while dose levels go up, but not in a linear way because it has a minimal level 0 and will reach a plateau when dose is very high. It is anticipated that RO7297089 would have a similar dose-DLT relationship.

## Appendix 11: Modified Continuous Reassessment Method with Escalation with Overdose Control Design

---

### Prior Setting

[figure not shown]
In particular, a minimal informative multiple normal prior (Neuenschwander et al. 2008) is utilized for  $\theta$  in the dose-escalation. It is conservatively assumed that it would be very unlikely (with a 95% confidence) that a 30% or higher and a 30% or lower DLT rates are associated with the starting dose, i.e., 60 mg, and the 1650 mg dose, respectively. The parameters of the minimal informative prior are listed below:

$$\mu = (0.2098152, 0.7905444)$$

$$\Sigma = \begin{pmatrix} 2.3807734 & 0.32675892 \\ 0.3267589 & 0.07025577 \end{pmatrix}$$

The prior distribution is displayed in [Figure 1](#), which is consistent with what is assumed: it would be unlikely that a 60 mg dose corresponds to a 30% or higher DLT rate, and a 1650 mg dose corresponds to a 30% or lower DLT rate.

Figure 1 Prior Distribution of the mCRM-EWOC Design

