### **The mCRM-EWOC Algorithm**

Patients in the first cohort will be treated with the starting dose. Prior to open a new cohort, the available DLT data will be used to update the mCRM-EWOC model through a Bayesian approach. That is, the posterior probability of parameter  $\theta$  from the logistic model will be estimated by using the DLT data from all eligible patients who complete the DLT observation period. A recommended dose,  $d_r$ , for the next cohort will be calculated using the updated mCRM-EWOC model, i.e.,  $P(d_r)\text{overdose} < 25\%$  and

$d_r = \min(d_{\max}, \max\{d_i: P(p(d_i) \in [0.2, 0.35])\})$  where  $d_{\max}$  is the highest next dose subject to the maximal increment rule.

Patients in the next cohort will be treated at the dose recommended by such an algorithm (possibly reduced based on clinical judgment). This process is repeated until the stopping criterion is met.

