### Hypothetical Trials

Several hypothetical trials are reported here to illustrate the behavior of the design in specific situations.

The first scenario illustrates how dose will be escalated assuming no DLTs are observed. The mCRM-EWOC model considered doses under a dose grid of every 5 mg from 60 mg to 100 mg and then every 10 mg up to 1650 mg.

[Table 1](#) shows the different levels suggested by the mCRM-EWOC design. The results show that, in the absence of observed DLTs, the design will reach high doses based in 4 cohorts.

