**Table 1 Dose Escalation Path in Absence of Observed DLTs**

Current Cohort Dose (mg)	Recommended Next Dose Increment % If No DLTs In Current Cohort
60	200
180	178
500	136
1180	36
1600	3
1650	

Additionally, the impact on dose-escalation of the occurrence of a first DLT is examined for all possible DLT frequencies (1 to 3, when the cohort size is 3) assuming that no DLTs occur until the given dose. The recommended next doses suggested by the design after the DLTs are reported in [Table 2](#).

The results show that the design will adequately adapt the dose in the presence of observed DLTs.

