**Table 2 Impacts on Dose-Escalation of the Occurrence of First DLTs**

[figure not shown]
First DLT at Dose	DLTs/cohort size	Next Dose	Increment (%)
60	1/3	100	67
	2/3	40	-33
	3/3	25	-58
180	1/3	180	0
	2/3	95	-47
	3/3	60	-67
500	1/3	450	-10
	2/3	220	-56
	3/3	130	-74
1180	1/3	880	-25
	2/3	500	-58
	3/3	290	-75
1600	1/3	1650	3
	2/3	1110	-31
	3/3	530	-67

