**Simulations**

A simulation study is conducted to evaluate the operating characteristics (sample size, estimated MTD, number of patients treated, overdose, etc.) for the chosen design parameters (priors, reference dose, stopping rules).

Scenarios with different toxicity profiles are simulated with hypothetical MTDs from 60 mg (low MTD) to >1650 mg (illustrating a scenario for which no toxicities are expected). The dose grid in simulations is set as 60 mg to 100 mg by 5 mg as a unit followed by increments of 10 mg all the way up to 1650 mg. The starting dose is 60 mg. Simulations are conducted based on 3-patient cohorts throughout the entirety of the study.

Figure 2 “True” Scenarios Used for Simulations

Each scenario uses 1000 simulated trials, analyzed by generating a MCMC chain run for 15000 iterations following a 5000-iteration burn-in period. Every one out of 2 iterations are saved after the burn-in i.e., step=2. Random manual checks revealed no significant MCMC convergence issues using standard convergence diagnostics.

The design is evaluated using the following criteria: the MTD chosen, the number of subjects treated at doses higher than the MTD and the sample size of the trials. The following table demonstrates the simulation study result.

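### Appendix 11: the dose-toxicity model and prior as printed give neither the stated 95% property nor the doses in Tables 1 and 2

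*Combined protocol and SAP*

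**What the plan says.** Appendix 11, Dose-Response Model, states that "The probability of DLTs over doses (dose-DLT response curve) will be described by a two-parameter logistic regression model". The formula shown is logit p(d) = alpha + beta(d/d*), with d* = 1200 mg and (alpha, log beta) bivariate normal.

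Prior Setting gives the mean (0.2098152, 0.7905444), the variances 2.3807734 and 0.07025577, and the covariance 0.32675892. It describes the prior as conservative: it is "very unlikely (with a 95% confidence) that a 30% or higher and a 30% or lower DLT rates are associated with the starting dose" of 60 mg and the 1650 mg dose respectively. It then says the prior figure agrees, "which is consistent with what is assumed: it would be unlikely that a 60 mg dose corresponds to a 30% or higher DLT rate", with the matching statement for 1650 mg.

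The design chooses the dose that maximises P(0.20 ≤ p ≤ 0.35) subject to P(p > 0.35) < 0.25 and a 3-fold cap. Table 1 ("Recommended Next Dose Increment % If No DLTs In Current Cohort") gives the no-DLT path 60, 180, 500, 1180, 1600, 1650 mg. Table 2 ("Impacts on Dose-Escalation of the Occurrence of First DLTs") gives the next dose after 1, 2 or 3 DLTs in the first cohort of three to have any.

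On the grid, Hypothetical Trials says "The mCRM-EWOC model considered doses under a dose grid of every 5 mg from 60 mg to 100 mg", and Simulations says "The dose grid in simulations is set as 60 mg to 100 mg by 5 mg as a unit".

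**The concern.** Every input needed to check the prior statement and Tables 1 and 2 is printed, so the three parts of the appendix should agree. They appear not to. With a linear dose term, 60 mg contributes only 60/1200 = 0.05 of beta, so the DLT rate at the starting dose is governed almost entirely by alpha, whose prior mean is positive. That puts the prior median DLT rate at 60 mg above one half.

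This is the primary safety model of a first-in-human study. It guides escalation and defines the MTD, and Section 3.1.1.2 refers back to the Appendix 11 model and priors for review if another regimen is added. Anyone who codes it from the text gets recommendations different from those shown to investigators and ethics committees, and the claim that the prior is conservative cannot be relied on.

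**Working it through.** **Inputs** (all Appendix 11): mean, covariance and d* as above (SDs 1.543 and 0.265, correlation 0.80); target interval 0.20 to 0.35; overdose limit 0.25; 3-fold cap; ceiling 1650 mg; cohorts of 3. I read the stated property as at most 5% in each tail. logit(0.30) = −0.8473.

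**Prior tails as printed.** logit p(60) = alpha + 0.05·beta. At the prior medians, beta = exp(0.7905) = 2.205, so logit p(60) ≈ 0.2098 + 0.1102 = 0.320 and the median DLT rate is about 0.58. Two-dimensional numerical integration gives P(p(60) ≥ 0.30) = 77.2% and P(p(1650) ≤ 0.30) = 2.5%. P(p(60) > 0.35) is 72.6%. That figure describes the printed prior only and is not an algorithm decision, because "Patients in the first cohort will be treated with the starting dose" by rule.

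**Prior tails with log dose and beta itself normal.** These have a closed form, with x = log(d/1200):
- 60 mg: x = −2.9957. Mean = 0.2098 − 2.9957 × 0.7905 = −2.158. Variance = 2.3808 + 8.9744 × 0.07026 − 2 × 2.9957 × 0.32676 = 1.0535, SD 1.0264. z = (−0.8473 + 2.1584)/1.0264 = 1.277, so P(p ≥ 0.30) = 10.1%.
- 1650 mg: x = 0.3185. Mean = 0.4616, variance = 2.5960, SD 1.6112. z = (−0.8473 − 0.4616)/1.6112 = −0.812, so P(p ≤ 0.30) = 20.8%.
- The 95th percentile of p(60) is 38% and the 5th percentile of p(1650) is 10%. For 5% tails the first must be no more than 30% and the second no less than 30%.
- P(p(60) > 0.35) falls to 6.7%.

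**Four readings of the same mean and covariance.** The last column counts the 20 entries of Tables 1 and 2 matched within 15%.

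| Reading | P(p ≥ 30% at 60 mg) | P(p ≤ 30% at 1650 mg) | Entries within 15% |
|---|---|---|---|
| Linear dose, log beta normal (as printed) | 77.2% | 2.5% | 8 (6 have no admissible dose) |
| Log dose, log beta normal | 0.0% | 14.7% | 5–6 |
| Linear dose, beta normal | 76.0% | 12.3% | 5 (6 have no admissible dose) |
| Log dose, beta normal | 10.1% | 20.8% | 19–20 |

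A fifth reading, with dose centred as (d − 1200)/1200 and log beta normal, gives 16.5% and 13.3% and does not give the tables either. No reading tried meets both limits.

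**Recommended doses.** The posterior is the prior times the binomial likelihood, with earlier cohorts at 0/3. The grid was extended below 60 mg because Table 2 lists 40 and 25 mg. The first entry in each cell is Table 1 (0/3); the next three are Table 2 (1/3, 2/3, 3/3).

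| Current dose (mg) | Appendix 11 tables | As printed | Log dose, beta normal |
|---|---|---|---|
| 60 | 180 / 100 / 40 / 25 | 95 / none / none / none | 180 / 100 / 45 / 25 |
| 180 | 500 / 180 / 95 / 60 | 540 / 80 / none / none | 520 / 200 / 100 / 65 |
| 500 | 1180 / 450 / 220 / 130 | 970 / 480 / 140 / none | 1230 / 440 / 230 / 140 |
| 1180 | 1600 / 880 / 500 / 290 | 1520 / 980 / 600 / 320 | 1650 / 1020 / 510 / 310 |
| 1600 | 1650 / 1650 / 1110 / 530 | 1650 / 1470 / 1080 / 780 | 1650 / 1650 / 1010 / 600 |

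As printed, the posterior P(p(60) > 0.35) after 1/3, 2/3 and 3/3 at 60 mg is 61%, 90% and 99%, so no dose passes the 25% limit. Restoring a log to the dose term alone, with log beta kept, recommends 180 mg even after 3/3 DLTs at 60 mg.

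**Monte Carlo error.** Under log dose with beta normal, all 20 table entries fall inside the 95% Monte Carlo range at effective sample sizes of 500 or 1000, and 18 of 20 at 5000. The largest gap, 880 against 1020 mg, sits on a flat maximum: target probability is 0.356 at both 990 and 1020 mg.

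**Grid.** On a grid that starts at 60 mg, the best-fitting reading has no admissible dose after 2/3 or 3/3 at 60 mg, since P(p(60) > 0.35) is 33% and 64%. The 40 and 25 mg entries therefore need a lower grid that the appendix does not state.

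**The case against.** The formula reached us through text extraction, so a log may have been lost from the dose term, and the prior figure is not visible. This stands as a caution, but restoring that log alone fixes neither the tables nor the 1650 mg tail. The prior statement is tested against the printed mean and covariance, so the figure cannot rescue it.

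The best-fitting reading is not proven to be what was run. Only 5 of 20 entries match exactly and 11 within 5%. Of the 15 that differ, 13 lie above the printed dose and 2 below, a lean that pure simulation noise should not show. Reference doses of 1000 to 1150 mg fit about equally well. This also stands: the diagnosis is an inference from fit. It does not help the 95% statement, because with d* = 1100 the tails are 11.5% and 19.9%, and no d* from 300 to 1400 mg brings both to 5% under this reading.

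The 5% per tail is an interpretation, since the appendix prints no tail probability and its closing sentence says only that the events are unlikely. It is the natural meaning of 95% confidence, and 77% cannot be called unlikely under any.

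The 60 mg grid is stated for the no-DLT scenario and the simulations, not expressly for Table 2. That makes it a minor clarification.

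Finally, the sponsor does the programming, escalation is bounded by the 3-fold cap, Internal Safety Committee review and clinical override, and no decision is shown to have been wrong. Section 5.1.1.1 reports Cohort 2 at 180 mg, the Table 1 step, although the cap alone would also allow it. These safeguards limit harm; they do not make the printed model, the prior statement and the tables agree.

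**Conclusion.** The concern holds and needs correcting. As printed, the prior gives 77% where about 5% is claimed at 60 mg, and the printed model does not generate Tables 1 and 2: six of the 20 entries have no admissible dose. The likely fault is a misprinted model and parameterisation rather than wrong tables. Even on the best-fitting reading, the chance of a DLT rate of 30% or more at 60 mg is about twice the 5% implied (10.1%), and the chance of 30% or less at 1650 mg about four times (20.8%).

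Confidence is high that text and tables disagree as printed, and moderate about which specification was run. The result assumes 5% per tail, the printed mean and covariance, d* = 1200 mg and cohorts of three. Table 3 was not tested, because its scenario curves are in a figure not shown.

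**What to change.** - Print the model actually run: d/d* or log(d/d*), and whether (alpha, beta) or (alpha, log beta) is normal, with the matching mean, covariance and d*.
- Replace the 95% statement with the true tail probabilities (about 10% and 21% if log dose with normal beta was run), or re-derive the prior so that each tail is at most 5%.
- State the grid used for Table 2 and reconcile it with the 60 mg lower end given in Hypothetical Trials and Simulations.
- Confirm from the R code that Tables 1 to 3 came from that specification, and regenerate them only if they did not.

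The cost is appendix wording and a check of the existing script. A re-run is needed if that check fails, or if the sponsor chooses to re-derive the prior, which is the dearer option and not required to make the text correct. No patients or new data are needed.
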